5.2 Definition of Dose Limiting Toxicity

5.2.1 Definition of dose limiting toxicities (DLT):

Toxicities will be graded according to the CTCAE version 4.0. If multiple toxicities are seen, the presence of DLT should be based on the most severe toxicity experienced. DLT will be defined as any of the following events occurring during treatment with temsirolimus and perifosine and attributable (possible, probable, or definite) to either study drug or the combined therapy:

- Any grade 3 thrombocytopenia, grade 4 anemia, and/or grade 4 neutropenia.

Amended:

Reviewed by OCR, JR 3/24/14

- Any unacceptable grade 2 non-hematologic toxicity, despite maximal medical treatment, that results in dose interruption of greater than 7 days within the first 28 days.*
- Any non-hematologic grade 3 or 4 toxicity, excluding alopecia, despite maximal medical treatment.*
- Failure to recover from toxicities to be eligible for re-treatment with temsirolimus and perifosine within 2 weeks of the last dose of temsirolimus and perifosine.

*Non-hematologic toxicities diarrhea and mucositis will only be considered a DLT if they remain grade 3 or unacceptable grade 2, despite maximal medical therapy.

*Hypercholesterolemia and hypertriglyceridemia and other Metabolism and Nutrition Disorders (such as hypophosphatemia and hypocalcemia) will only be considered a DLT if they remain grade 3 or unacceptable grade 2, despite maximal medical therapy

5.2.2 Maximum Tolerated Dose (MTD)

The MTD will be based on the assessment of DLT during the first 28 days of treatment only (cycle 1). Escalations are planned in groups of three patients, with an additional three patients to be added at the first indication of Dose Limiting Toxicity (DLT). (Please see next two paragraphs). **There is NO intra-patient dose escalation.** The MTD of temsirolimus in combination with perifosine will be defined as the dose at which fewer than one-third of patients experience a DLT. Therefore, the MTD is the dose level at which 0/3 or 1/6 (or up to 2/9, etc.) patients experience DLT with the next higher dose having at least 2/3 or 2/6 patients encountering DLT. Up to three patients may be enrolled simultaneously at each dose level. These patients should be observed for DLT for at least 4 weeks from the first day of treatment before new patients are enrolled at the next highest dose level ([Table 2](#)). Patients completing 28 days of therapy or patients removed for toxicity earlier than 28 days are evaluable. Patients removed from study within 28 days for reasons other than toxicity may be replaced.

Table 2: Dose levels used to determine dosing for specific cohorts in the Phase I component

Dose level	Temsirolimus (mg/week)	Perifosine load/maintenance (mg/day)
-6	5	150/50
-5	10	150/50
-4	15	150/50
-3	15	150/100
-2	15	300/100
-1	15	450/100
1 (starting)	15	600/100
2	25	600/100
3	50	600/100
4	75	600/100
5	115	600/100
6	170	600/100
7	170	900/100

The following dose escalation rules will be used:

- Three patients are studied at the first dose level
- If none of these three patients experience DLT, then the dose is escalated to the next higher level in the three subsequent patients.
- If one of the three patients experience DLT at the current dose, then three more patients are accrued at the same dose. If none of these three additional patients suffer DLT, then the dose is escalated in subsequent

Amended:

Reviewed by OCR, JR 3/24/14

patients. If one or more of these three additional patients experiences DLT, the MTD has been exceeded and three more patients are treated at the next lower dose (if only three patients were previously treated at that prior dose).

- If two or more patients encounter DLT, then the MTD has been exceeded and three more patients are treated at the next lower dose level (if only three patients were previously treated at that prior dose).
- At least 6 patients will be treated at the MTD.
- All escalations will occur in separate cohorts. There is no intra-patient dose escalation of either drug.

Table 3: Escalation rules

Number of Patients with DLT at a Given Dose Level	Escalation Decision Rule
0 out of 3	Enter 3 patients at the next dose level.
≥ 2	Dose escalation will be stopped. This dose level will be declared the maximally administered dose (highest dose administered). Three (3) additional patients will be entered at the next lowest dose level if only 3 patients were treated previously at that dose.
1 out of 3	Enter at least 3 more patients at this dose level. 
• If 0 of these 3 patients experience DLT, proceed to the next dose level.• If 1 or more of this group suffer DLT, then dose escalation is stopped, and this dose is declared the maximally administered dose. Three (3) additional patients will be entered at the next lowest dose level if only 3 patients were treated previously at that dose. However, a cohort may be expanded to more than 6 patients if the PI and CTEP medical monitor agree more information is needed to clarify whether a DLT has occurred or the MTD has been reached.
≤ 1 out of 6 at highest dose level below the maximally administered dose	This is generally the recommended phase 2 dose. At least 6 patients must be entered at the recommended phase 2 dose.

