5.3 General Concomitant Medication and Supportive Care Guidelines

- 5.3.1 Nausea/vomiting - [see 5.1.1](#)
- 5.3.2 Hyperuricemia/gout – [see 5.1.1](#)
- 5.3.3 Hypersensitivity reactions – [see 5.1.1](#)
- 5.3.4 Mucositis - Mucositis is common with CCI-779 (temsirolimus). This can be troublesome in the initial few weeks but usually subsides with time. Early treatment with mouthwash is recommended (e.g. Magic mouth wash (Maalox, viscous lidocaine and benadryl in 1:1:1 mixture) or kaopectate/ diphenhydramine/ lidocaine solution in 1:1:1 mixture). Antifungal agents should be used if oral candidiasis is present. Consider GI consultation.
- 5.3.5 Hyperlipidemia - It is recommended that patients with hyperlipidemia be treated with pravastatin (which dose not affect cytochrome metabolism), extended release niacin, or gemfibrozil (Lopid),

Amended:

Reviewed by OCR, JR 3/24/14

such as Lopid 600 mg BID.

5.3.6 Diarrhea should be managed with loperamide: 4 mg at first onset, then 2 mg every 2-4 hours until diarrhea is controlled (maximum = 16 mg loperamide/day). Additional antidiarrheal measures may be used at the discretion of the treating physician as warranted by the patient's condition. Consider GI consultation.

5.3.7 Routine supportive measures for cancer patients such as erythropoietin, analgesics, blood transfusions, antibiotics, bisphosphonates, and hematopoietic colony stimulating factors for treatment of cytopenias are permitted.

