6.1.2 Hematologic Toxicity

No dose adjustment or reduction of perifosine will be made for hematologic toxicity.

Dose Modifications of CCI-779 (Temirolimus) Based on Weekly ANC and Platelet Counts:

ANC (/mL)	Platelets (/mL)	% of Planned temsirolimus
≥ 1000	and ≥ 75,000	100%
750-999	or 50,000 to < 75,000	hold*
< 750	or < 50,000	hold**

* Upon recovery to ANC \geq 1,000/mL and platelets to \geq 100,000/mL, one lower dose level of temsirolimus will be administered (See [Table 4](#)). Patients already at the lowest dose level (5 mg i.v. weekly) will be removed from study.

** Upon recovery to ANC \geq 1,000/mL and platelets to \geq 100,000/mL, two lower dose levels will be administered. The exception will be patients at dose level -1 (10 mg i.v. weekly) who will be dose-reduced by only one level to 5 mg IV weekly (See [Table 4](#)). Patients already at the lowest dose level (5 mg i.v. weekly) will be removed from study.

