6.1.3 Non-hematologic toxicity

Dose Modifications Based on perifosine and temsirolimus-related Non-Hematologic Toxicities and dose adjustments for each drug shown in [tables 4, 5, and 6](#):

NCI Grade	% of Planned perifosine and temsirolimus dose
0-2+	100%+
3*	hold**
4	hold***

- + For symptomatic Grade 2 toxicity, the dose may be held until recovery to CTC Grade 0-1, then continue at the same dose or reduce by one level of temsirolimus and/or perifosine at the investigator's discretion. Grade 2 diarrhea does not require temporary discontinuation of treatment as this toxicity may improve despite continued treatment. For grade 2 diarrhea that is unacceptable to the patient for symptomatic reasons, hold perifosine temporarily held until resolution \leq grade 1 and subsequently re-started at the same dose. If symptomatic grade 2 diarrhea recurs after re-instituting treatment at the same daily dose and require temporary discontinuation, treatment of both agents should be held until resolution to \leq grade 1 and re-instituted at a reduced doses of both agents (see [Table 4, 5, and 6](#)).
- + In addition, areas of intratumoral micro-hemorrhage were noted on necropsy of mice harboring modeled GBMs following combined treatment of perifosine and temsirolimus. Significance of this in humans is unclear, and it may represent an early response to therapy. However, for patient safety, a non-contrast head CT or MRI with gradient echo imaging is required during the 2nd week of therapy to evaluate for such microbleeds. CTCAE grade 1 (asymptomatic, radiographic findings only) do not require treatment modification. CTCAE grade 2 (medical intervention indicated) may require corticosteroids as treatment for associated edema or other intervention at the discretion of the investigator, but treatment can continue at the discretion of the investigator.

Memorial Sloan Kettering Cancer Center
IRB Protocol

IRB#: 09-058 A(14)

- * Except nausea/vomiting (unless patients are on maximal antiemetic therapy) or hypercholesterolemia and hypertriglyceridemia and other Metabolism and Nutrition Disorders (such as hypophosphatemia and hypocalcemia) unless remaining grade 3 or unacceptable grade 2, despite maximal medical therapy.

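### A patient whose temsirolimus is held and lowered for an ANC of 500–999 in cycle 1 is still scored as DLT-free at the full assigned dose

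*Combined protocol and SAP*

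**What the plan says.** **DLT definition (5.2.1).** The hematologic criterion is "Any grade 3 thrombocytopenia, grade 4 anemia, and/or grade 4 neutropenia". Table 7 puts grade 4 neutrophils at an ANC below 500 and grade 3 at 500–1,000. Grade 2 non-hematologic toxicity is a DLT if it is unacceptable despite maximal treatment in a way "that results in dose interruption of greater than 7 days within the first 28 days". Failure to recover enough for re-treatment within two weeks of the last dose is also a DLT. A dose reduction or a missed dose is not itself on the list.

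**Who is counted (5.2.2 and 13.1).** The MTD rests on DLTs in the first 28 days. "Patients completing 28 days of therapy or patients removed for toxicity earlier than 28 days are evaluable". For replacement: "Patients removed from study within 28 days for reasons other than toxicity may be replaced". No minimum number of doses or share of the planned dose is required.

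**Dose changes inside the cycle (section 6).** The study design text in 2.4 applies section 6 to phase I, and 5.1.3.2 schedules weekly counts for the first four weeks. Under 6.1.2, an ANC of 750–999 means a hold and then one level down. Below 750 it means a hold, after which "two lower dose levels will be administered". Section 6.1.1 bars re-escalation of doses reduced for drug-related toxicity. For symptomatic grade 2 non-hematologic toxicity, 6.1.3 lets the investigator hold and "then continue at the same dose or reduce by one level of temsirolimus and/or perifosine".

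**The concern.** The thresholds for lowering a dose and for calling a DLT differ, and the evaluability rule does not say what happens between them. A patient in that gap is moved to the dose of a lower cohort for the rest of cycle 1, stays on study, completes 28 days and enters the escalation count as a patient without DLT at the higher dose.

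The MTD is the phase I primary objective. It sets the phase II starting dose (5.1.1.6), and qualifying phase I patients treated at the MTD enter the phase II efficacy analyses (11.1, 13.2). If the patients behind a result of 0/3 or 1/6 did not stay on the assigned dose, that result says less about its tolerability than the rule assumes.

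**Working it through.** **Step 1: the plan's own figures.** With true DLT rate p, the design escalates on 0/3, or on 1/3 followed by 0/3:

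P(escalate) = (1−p)³ + 3p(1−p)² × (1−p)³

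| p | 10% | 20% | 30% | 40% | 50% | 60% |
|---|---|---|---|---|---|---|
| Section 13.1 | .91 | .71 | .49 | .31 | .17 | .08 |
| Recomputed | .906 | .709 | .494 | .309 | .172 | .082 |

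All six agree. The table is right for DLTs as listed; the question is what the listed DLT leaves out.

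**Step 2: the gap on neutrophils.**

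| ANC in cycle 1 | Section 6.1.2 | Table 7 | DLT under 5.2.1? |
|---|---|---|---|
| 750–999 | hold, one level down | grade 3, one level down | no |
| 500–749 | hold, two levels down | grade 3, one level down | no |
| below 500 | hold, two levels down | grade 4, two levels down | yes |

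For 500–749 the two places disagree on the size of the cut. Table 7 sits under the next-cycle heading (6.1.4), but the text introducing it bases hematologic adjustments on counts taken for the day of treatment, so it is not clearly confined to cycle starts. Under either place the dose falls and no DLT is recorded.

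**Step 3: dose received.** Assume weekly doses on days 1, 8, 15 and 22: day 1 in full, day 8 held for an ANC of 500–999, recovery by day 15, and days 15 and 22 at the reduced level. Day 15 is 14 days after day 1, so the two-week recovery criterion is met. With Table 4 doses, share = (full + 0 + 2 × reduced) / (4 × full):

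| Assigned (mg) | One level down | Two levels down |
|---|---|---|
| 15 | 35/60 = 58% | 25/60 = 42% |
| 25 | 55/100 = 55% | 45/100 = 45% |
| 50 | 100/200 = 50% | 80/200 = 40% |
| 75 | 175/300 = 58% | 125/300 = 42% |
| 115 | 265/460 = 58% | 215/460 = 47% |
| 170 | 400/680 = 59% | 320/680 = 47% |

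These are early-onset figures. At 75 mg, a first hold on day 15 gives (75 + 75 + 0 + 50)/300 = 67% or (75 + 75 + 0 + 25)/300 = 58%. A first hold on day 22 gives 225/300 = 75%, with the reduction falling after cycle 1.

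**Step 4: illustrative effect on escalation.** Let p be the listed-DLT rate and q the further share of all patients reduced in cycle 1 without a DLT. The documents do not give q. Take p = 10% and q = 20, 30 or 40%.

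- As written: p = 10%, P = 0.91 whatever q is.
- If reductions were counted as events: p + q = 30, 40 or 50%, P = 0.49, 0.31 or 0.17.
- If reduced patients were instead replaced: the rate among the rest is p/(1−q) = 12.5, 14.3 or 16.7%, P = 0.86, 0.83 or 0.78.

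The last line shows that replacement alone recovers little, because it keeps the patients who tolerated the dose.

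**The case against.** DLT and dose-modification thresholds need not coincide, and the protocol separates them knowingly: a footnote in 6.1.3 sets no minimum hold unless the event is a DLT. There are also safeguards. A cohort may be expanded if the PI and the CTEP medical monitor want more information, at least six patients are treated at the recommended dose, adverse events are reviewed at least weekly in cycle 1, and 13.1 has dose modifications described. This is fair, but expansion is discretionary and the reporting is descriptive. Neither changes how a reduced patient is scored.

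It could be said that completing therapy implies completing it at the assigned dose. The text does not say so, and perifosine continues unchanged through hematologic toxicity (6.1.2), so the patient remains on therapy. Section 13.1 mentions first-cycle cessation before DLT, not reduction.

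Several stronger readings are tempting but not supported:

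- *Patients given growth factors or transfusions are also wrongly counted.* Section 5.3.7 says only that "hematopoietic colony stimulating factors for treatment of cytopenias are permitted". The protocol does not treat supported patients as intolerant, and a cytopenia that reaches DLT grade counts whether or not it is supported.
- *Platelets show the same gap.* Table 7 labels 50,000–75,000 as grade 3, which would be a DLT under 5.2.1. Because 5.2.1 itself defers to CTCAE 4.0, this route is unclear.
- *Grade 2 reductions are as firm a route as neutrophils.* The reduction in 6.1.3 is discretionary, interruptions over 7 days already count, and a footnote in 5.2.1 addresses diarrhea and mucositis that stay unacceptable at grade 2.
- *20–40% of patients will be reduced.* Nothing supports that rate. Section 7.1.1 lists neutrophil decrease for temsirolimus among events at or below 20%. The chance that all three patients in a cohort are such cases is q³, or 0.8% at q = 20% and 6.4% at q = 40%.

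**Conclusion.** The point holds for neutrophils on the documents alone. An ANC of 500–999 in cycle 1 brings a required temsirolimus reduction, no DLT, and full credit as DLT-free at the assigned level. With an early low count the patient has received 40–59% of planned cycle 1 temsirolimus, assuming a day 8 hold and recovery by day 15; later onset gives a larger share. A discretionary grade 2 reduction after an interruption of 7 days or less can have the same effect.

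The gap does not depend on how often this happens, but its effect on the MTD does, and that frequency is not given. The fall from 0.91 to 0.49, 0.31 or 0.17 is a what-if calculation, not a forecast. A reader might infer that the escalation table in 13.1 is wrong or that the MTD will be too high. The table is correct for DLTs as defined, and the documents do not show how far the MTD would move.

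**What to change.** Reconcile 5.2.1, 5.2.2 and 13.1 with 6.1.2, 6.1.3 and Table 7:

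- Make evaluability as DLT-free depend on the cycle 1 dose actually received at the assigned level, with the minimum set by the sponsor and CTEP. A patient reduced for drug-related toxicity should not simply be scored as DLT-free at the higher dose.
- Treat patients under-dosed for reasons other than toxicity as non-evaluable and replaceable.
- State how toxicity-related reductions enter the escalation count. That choice belongs to the sponsor and CTEP, but simple replacement would select tolerant patients.
- Reconcile 6.1.2 and Table 7 for an ANC of 500–749, and the Table 7 platelet grade with 5.2.1.

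The cost is protocol wording, an occasional extra patient per cohort, and possibly a lower MTD. That last cost depends on the rule chosen and should be weighed when it is set.

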5.3 General Concomitant Medication and Supportive Care Guidelines

- 5.3.1 Nausea/vomiting - [see 5.1.1](#)
- 5.3.2 Hyperuricemia/gout – [see 5.1.1](#)
- 5.3.3 Hypersensitivity reactions – [see 5.1.1](#)
- 5.3.4 Mucositis - Mucositis is common with CCI-779 (temsirolimus). This can be troublesome in the initial few weeks but usually subsides with time. Early treatment with mouthwash is recommended (e.g. Magic mouth wash (Maalox, viscous lidocaine and benadryl in 1:1:1 mixture) or kaopectate/ diphenhydramine/ lidocaine solution in 1:1:1 mixture). Antifungal agents should be used if oral candidiasis is present. Consider GI consultation.
- 5.3.5 Hyperlipidemia - It is recommended that patients with hyperlipidemia be treated with pravastatin (which dose not affect cytochrome metabolism), extended release niacin, or gemfibrozil (Lopid),

Amended:

Reviewed by OCR, JR 3/24/14

such as Lopid 600 mg BID.

5.3.6 Diarrhea should be managed with loperamide: 4 mg at first onset, then 2 mg every 2-4 hours until diarrhea is controlled (maximum = 16 mg loperamide/day). Additional antidiarrheal measures may be used at the discretion of the treating physician as warranted by the patient's condition. Consider GI consultation.

5.3.7 Routine supportive measures for cancer patients such as erythropoietin, analgesics, blood transfusions, antibiotics, bisphosphonates, and hematopoietic colony stimulating factors for treatment of cytopenias are permitted.

5.3.8 CY450 metabolism - In vitro studies with Temsirolimus in human liver microsomes indicate that CYP3A4 may be the primarily enzyme responsible for the agent's metabolism, suggesting that compounds known to modulate CYP3A4 activity may therefore affect the metabolism of Temsirolimus. Inhibitors of CYP3A4 may decrease the metabolism and increase Temsirolimus levels, while inducers of CYP3A4 may increase the metabolism and decrease Temsirolimus levels. Temsirolimus or its metabolites may also interact with the CYP450 enzyme system by inhibiting CYP2D6. Because there is a potential for interaction of temsirolimus and potentially perifosine with other concomitantly administered drugs through the cytochrome P450 system, the case report form must capture the concurrent use of all other drugs, over-the-counter medications, or alternative therapies. The Principal Investigator should be alerted if the patient is taking any agent known to affect or with the potential to affect selected CYP450 isoenzymes. **Every effort should be made to avoid cytochrome P450 inducing medications. Please see [Appendix B](#) and [Appendix C](#).**

5.3.9 Therapeutic anticoagulation - Patients on therapeutic anticoagulation should have PT/INR or PTT (whichever is appropriate) monitored closely during therapy (e.g., weekly for the first month and weekly for a minimum of 2 weeks following discontinuation of the agent). Therapy should be held if the coagulation parameters are higher than the intended therapeutic range.

5.3.10 Corticosteroids should be used in the smallest dose to control symptoms of cerebral edema and mass effect, and discontinued if possible.

5.3.11 Anti-seizure medications should be used as indicated. **IT IS STRONGLY RECOMMENDED THAT EVERY EFFORT SHOULD BE MADE TO MAINTAIN THE PATIENT ON A NON-EIAED RATHER THAN EIAED IF ANTI-SEIZURE PROPHYLAXIS IS REQUIRED. (APPENDIX B).**

5.3.11.1 Patients who were previously on a non-EIAED and need to change anticonvulsants, should be started on another non-EIAED if at all possible. No delays in treatment would be required.

5.3.11.2 Patients who were previously on a either no AED or a non- EIAED and started on an EIAED should immediately be started on another non-EIAED and the EIAED discontinued/tapered off as quickly as possible. The patient may continue the current treatment dose while a non-EIAED is re-started.

5.3.11.3 Patients who were previously on a non-EIAED and need to permanently change anticonvulsant, but who cannot change to another non-EIAED **MUST BE DISCUSSED WITH THE STUDY PI OR CO-PI.** These patients will be taken off-study unless it is felt that they have benefited from the therapy following assessment by the investigator, PI, and CTEP medical monitor. In some cases, this may be associated with an increase in the dose(s) used.

Amended:

Reviewed by OCR, JR 3/24/14

5.3.12 Other Concomitant Medications - Therapies considered necessary for the well being of the patient may be given at the discretion of the investigator. Other concomitant medications should be avoided except for analgesics, chronic treatments for concomitant medical conditions, or agents required for life-threatening medical problems. All concomitant medications must be recorded.

5.3.13 Surgery - If neurosurgical or other surgical management is required for reasons not due to tumor progression, these procedures must be documented, including the indications for surgery, the surgical operative note and pathology report.

5.3.14 Other Anticancer or Experimental Therapies - No other anticancer therapy (including chemotherapy, radiation, hormonal treatment or immunotherapy) of any kind is permitted during the study period. No other drug under investigation may be used concomitantly with the study drug. If patients are subsequently found to have been taking such therapy before or during initiation of study treatment, the patient can be replaced and will not be included in toxicity or efficacy analyses following discussion by the investigator, PI, and CTEP medical monitor.

